4. STUDY DESIGN

This is an interventional pilot study based on the community stakeholder-derived data from three previous Quality Improvement projects to improve the partnership between CCHMC, CPS, and CHD to reduce the morbidity of childhood asthma in the inner city schools of Cincinnati and CCHMC. About 30 high-risk asthmatic participants will be identified to participate and a number of interventions will be incorporated including asthma specific questionnaires, use of a commercially available inhaler cap monitoring sensor, a mobile software management platform that tracks adherence of all asthma medications, mobile based telehealth medical visits to assess asthma control, and mobile based telehealth adherence problem-solving interventions.

This proposal is funded through a Luther Foundation and Verizon Foundation philanthropic gifts.

5. DURATION:

Duration for the participants will be 6 months. Participants will be enrolled in the study during the first year of the project. If necessary to complete enrollment the enrollment period will extend into the second school year. Data analysis will be performed 3 months after the last participant completes the project.

6. SELECTION & RECRUITMENT OF PARTICIPANTS:

A. Number of participants

Patient Population: 30 middle-schoolers/adolescents that attend a participating CPS (Oyler, Roberts, Withrow, and School of Creative and Performing Arts schools) will be recruited for a 6 month pilot study of testing the feasibility of a novel, school-based care delivery system to improve asthma outcomes. Given the relationship of the CCHMC Asthma Center with CPS and the CHD in our ongoing quality improvement work, the study investigators have contacts with the school staff, school nurses, and primary care providers associated with the following CPS (Oyler, Roberts, Withrow, and School of Creative and Performing arts). As part of this work, our team also helps the school nurses screen children with asthma to identify those with uncontrolled asthma and help the nurse's contact families to encourage them to establish or connect with an existing medical home to schedule an asthma visit and to obtain asthma medication.

B. Inclusion/Exclusion criteria

Inclusion

- age 10-17 years; history of provider-diagnosed asthma;
- history of uncontrolled asthma in the past 12 months (two ACT scores <20; ≥ 1 UC/ED visit or hospitalization for asthma, ≥ 2 prednisone bursts) with current persistent asthma as defined by NAEPP guidelines,

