The subject or the subject and his or her parent will be given the consent for the study and it will be reviewed and time given for questions. The subject will sign the assent or consent after all questions are answered and a signed copy of the consent form will be given to the subject to keep. The subject will be informed that this research is voluntary and that they are able to withdraw at any time. No study related procedures will be done prior to consent being signed.

For participants under age 18, age of assent will be determined by the IRB and those assenting will sign after all questions are answered.

For non-English speaking participants

Because this is a small pilot and heavily dependent on English fluency for teleconference interviews and questionnaires, only participants who are fluent in English will be enrolled. If a parent is non-English speaking, the PI will determine if the subject can be enrolled based on subject's fluency. If a non-English speaking parent will be giving Parental

Permission, the research team will use a short form consent process as per CCHMC SOP 41-1.8. The approved long consent form will serve as the summary of the research.

8. STUDY PROCEDURES:

Visit	Screening Phone call	Visit 1	Visit 2	Self-Management Visit 1	Visit 3	Self-Management Visit 2	Self-Management Visit 3	Visit 4	Self-Management Visit 4	Self-Management Visit 5	Visit 5	Visit 6	Visit 7	
Time		Day 1	Month 1	Month 1½	Month 2	Month 2	Month 2½	Month 3	Month 3	Month 3½	Month 4	Month 5	Month 6	
Place	H/CCHMC / SNO/ SHC			SNO/SHC	SNO/SHC	SNO/SHC	SNO/SHC	SNO/SHC	SNO/SHC	SNO/SHC				
Procedures														
Telehealth visit	x		x	x	x	x	x	x	x	x				
Motivational Interview			x	x	x	x	x	x	x	x				
Questionnaires	x	x		x				x			x	x	x	
Asthma education	x													
ACT	x	x		x			x			x	x	x		
TreatSmart (Web Based)											x	x	x	
Prescriptions as needed	x	x		x			x			x	x	x		
Review Smart Cap use		x		x			x		x		x	x	x	
Dispense smart phone and preloaded data plan	x													
Dispense propeller Health cap	x													
Propeller Health system education/load on smart phone			x											

H=Home
SNO=School Nurse Office
SHC=School Health Clinic

The study length is 6 months. 30 participants will be enrolled over 3 months during the 2015-2016 school year. Propeller, TreatSmart program and ACT screenshots are located in the Appendix.

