procedures for informing parent/guardians of their options, and adhering to parent/guardians' wishes, while not compromising the integrity of the study. Hence, the smart phones will be loaded with a security software program Air Watch and include a basic package of social media apps that middle-schoolers and adolescents frequently use. We will list out for the parent/guardians that apps are installed on the phone and brief descriptions of the risks and benefits and they will be told this is similar to their teen's current cell phone. After being informed, parent/guardians and participants will then be given an instruction sheet (See Appendix B) on how to use the cell phone. Within this instruction sheet there will be instructions on how to add apps by using the family's apple ID account or removing apps from the cell phone if the participants or parent/guardian desire. However, CCHMC IT will be alerted if the Propeller Health app is removed from the phone. The Air Watch security software enforces specific security measures, such as passcode and encryption. The study team working with the CCHMC IT department will be able to erase all content in the event of a lost/stolen device. The Air Watch security software does not monitor the participants' usage or personal information. Internet access on the smartphone is being restricted with Apple's built in Adult Content Filter for the Safari web browser. This content filter does its best to block websites with inappropriate content. The Internet content filter can identify, with a high degree of accuracy, whether a Web page is safe or not by examining various properties of the website including text and structure. The content filter is being managed by the Air Watch security software and cannot be removed.

13. RISK/BENEFIT ANALYSIS:

This study is minimal risk with direct benefit to the participants. It builds on the CCHMC-CPS-CHD existing asthma QI program to improve asthma care and it provides more comprehensive asthma management and monitoring than many of these participants currently receive.

14. DATA SAFETY & MONITORING:

DSMP:

The Data Safety and Monitoring Plan (DSMP) will consist of a Steering Committee made up of [name] and key study personnel. The committee will meet annually to review adverse events and to provide oversight and coordination of project management, research administration, publications and data sharing, and integration of all resources needed for the project.

Adverse Events:

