6. Important medical events that may not result in death, be life threatening, or require hospitalization may be considered serious when, based upon appropriate medical judgment, they may jeopardize the subject and may require medical or surgical intervention to prevent one of the outcomes listed above.

Wheezing episodes and exacerbations of asthma are anticipated events in the population under study even when receiving standard of care therapy. A hospitalization for wheezing or asthma will not be recorded as an SAE unless it is considered a serious and unexpected suspected adverse reaction SUSAR (9.3.2). All other hospitalizations will be recorded in the case reporting forms.

Review with family of possible adverse events will be done at medical visits and follow-up phone calls by the research coordinator if adverse events occur, will be documented. Adverse events will be recorded on an Adverse Event Reporting Form and will be reviewed at the meeting of the Steering committee.

If a parent/guardian response or complaint is not an expected adverse event (see section 4) or if the adverse event presents with greater than expected severity, the adverse event will be brought to the Investigator's attention in a timely manner for evaluation. The reviewing investigator will determine if the event is a Reportable Event as defined below.

Definition of Reportable Events

Reportable events must fall into one of the categories below:

1. Adverse event that is BOTH unexpected AND related or possibly related to participation in the research. This is regardless of whether internal or external site or seriousness.

2. An event that requires a change to the protocol or informed consent.
3. Information that indicates a change to the risks or potential benefits of the research.
4. Breach of confidentiality.
5. Change in labeling or withdrawal from marketing for safety reasons of a device used in research protocol.
6. Change to protocol made without prior IRB review to eliminate an apparent immediate hazard to a research participant.
7. Protocol violation that harmed a participant or others or indicates that participants or others are at increased risk of harm.
8. Incarceration of a participant in a protocol not approved to enroll prisoners.
9. Complaint of a participant that indicates unexpected risks or cannot be resolved by the research team.

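### With annual meetings, the Steering Committee's first adverse-event review can come after the last child has finished, because enrolment plus follow-up is planned to take about 9 months

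*Combined protocol and SAP*

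**What the plan says.** **Committee.** Section 14 (Data Safety & Monitoring, DSMP) sets up a Steering Committee that includes key study personnel and states: "The committee will meet annually to review adverse events". Under Adverse Events in the same section, events go on an "Adverse Event Reporting Form and will be reviewed at the meeting of the Steering committee". No first meeting date, interim meeting or event-triggered meeting is described.

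**Timeline.** Section 8 says "30 participants will be enrolled over 3 months during the 2015-2016 school year". Section 5 says "Duration for the participants will be 6 months". On enrolment, Section 5 is looser: "Participants will be enrolled in the study during the first year of the project", and "If necessary to complete enrollment the enrollment period will extend into the second school year".

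**Asthma hospitalisations.** The Section 14 definition of serious includes inpatient hospitalisation. Asthma exacerbations are then declared anticipated: "A hospitalization for wheezing or asthma will not be recorded as an SAE unless it is considered" a serious and unexpected suspected reaction (SUSAR). The next sentence reads: "All other hospitalizations will be recorded in the case reporting forms".

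**The concern.** The sponsor chose a committee to look at adverse events together, but on the Section 8 timeline the meeting interval is longer than the study. A review held after the last exit can describe what happened but cannot change conduct for any child.

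The event that most needs a cumulative look is worsening asthma. The children are selected for uncontrolled asthma (Section 6B), and their medication is reassessed monthly by telehealth (Section 8). A single admission may look unremarkable in this population, while several within a few weeks would not. The committee is the only body in the plan given the task of reviewing adverse events across participants, so its timing decides whether a cluster is reviewed while there is still time to act.

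**Working it through.** **Inputs**
- Enrolment period E = 3 months, N = 30 (Section 8)
- Follow-up F = 6 months per child (Section 5)
- Meeting interval = 12 months (Section 14)
- First meeting date: not stated. Assumed in steps 1 and 2 to be 12 months after first enrolment.

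The plan states no total duration, so there is no figure of its own to reproduce.

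**Step 1. Planned timeline.** Last exit = E + F = 3 + 6 = 9 months. A month-12 meeting is 12 − 9 = 3 months after the last exit. By then 30 of 30 children have finished, and all 30 × 6 = 180 child-months have accrued.

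**Step 2. Slower enrolment.** A month-12 meeting precedes the last exit only if E + 6 > 12, that is, if E > 6 months. With uniform enrolment (an assumption) and E of 6 months or more, the number finished by month 12 is 30 × 6/E.

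| E (months) | Last exit (month) | Finished by month 12 | Child-months by month 12 |
|---|---|---|---|
| 3 | 9 | 30 | 180 |
| 6 | 12 | 30 | 180 |
| 9 | 15 | 20 | 20 × 6 + 10 × 4.5 = 165 |
| 12 | 18 | 15 | 15 × 6 + 15 × 3 = 135 |
| 18 | 24 | 10 | 10 × 6 + 10 × 3 = 90 |

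**Step 3. Meeting date unrelated to study start.** Because 12 > 9, at most one annual meeting can fall within the 9 months. If the date is uniform over the year (an assumption), the chance that none does is 1 − 9/12 = 25%.

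**Step 4. Do other routes supply a cumulative review?**
- Prompt IRB reporting (Section 14) covers unexpected, related events. Exacerbations are declared anticipated.
- IRB reporting within 48 business hours covers serious, life-threatening events related to study procedures. It has no unexpectedness condition, but it works event by event.
- Other adverse events that arise during study procedures wait for a table at continuing review, whose interval is not stated.
- An event more severe than expected goes to the investigator in a timely manner, again one event at a time.
- Severe exacerbations are counted for each child at each medical visit, with an individual termination rule (Section 8).
- A daily sensor report flags individual children (Section 8). The study team is blinded to sensor data in month 1, so this report may not operate then.

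None of these is a scheduled review across children.

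**Step 5. Are asthma admissions on the case report form?** The sentence on other hospitalisations follows one that both names asthma admissions and exempts them from SAE status. It can mean every hospitalisation not for asthma, or every hospitalisation not classed as a SUSAR, which would include asthma. The text does not settle it. The TreatSmart screen in Appendix B does ask about overnight stays, emergency or urgent care, oral steroids and intensive care, but as undated counts over 12 months. In a 6-month study these mix events before and after entry.

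**The case against.** The case against is substantial, and parts of it stand.

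- **No anchor date.** A reader might infer that the committee cannot act in time for any child. The documents do not support that. The first meeting date is open, and if it were unrelated to study start, the chance of no meeting within the 9 months would be 25%, not certainty.
- **Enrolment may be longer.** A reader might infer that only the second-year contingency could place a meeting part-way. Section 5 already leaves the whole first project year open for enrolment, and any period over 6 months puts a month-12 meeting before the last exit.
- **Other oversight exists.** A reader might infer that nobody is watching, or that expedited reporting is confined to unexpected events. Neither is right, as the routes in step 4 show. The reportable-event list also includes information that changes the risks of the research, which could cover a cluster once someone had noticed it. One study team follows all 30 children, and the committee includes key study personnel, so its members need not be unaware of events before they meet.
- **Not an SAE does not mean unrecorded.** A reader might infer that asthma admissions are lost. Wheezing episodes are recorded as expected adverse events and on other study forms, so the text shows an ambiguity, not a proven gap.
- **Minimal risk.** Section 13 classes the study as minimal risk. There is no control group and no expected admission rate, so a listing would have no formal benchmark. This lowers the weight of the point.

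None of these arguments supplies a scheduled cumulative review while children are in the study. Informal awareness within the team is not the review that Section 14 promises.

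**Conclusion.** The point holds at moderate strength: following the plan as written can leave no committee review of adverse events while any child is enrolled. On the Section 8 timeline, with a first meeting 12 months after first enrolment, the review comes 3 months late for all 30 children. With uniform enrolment over 9 or 12 months it falls part-way, after 20 or 15 of the 30 have finished.

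The result rests on the meeting date assumed in step 1 and, for the part-way figures, on uniform enrolment. It concerns the timing of cumulative review and the clarity of hospitalisation recording. It does not show that safety monitoring is absent, and it does not affect the validity of the efficacy analysis. It is a cheap improvement.

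**What to change.** 1. In Section 14, replace the annual schedule with reviews timed to the study, for example the first about 3 months after first enrolment and then every 3 months until the last Visit 7. The 3-month interval is a suggestion, not a figure derived from the documents. With uniform 3-month enrolment, reviews at months 3, 6 and 9 would see about 30 × 1.5 = 45, 30 × 4.5 = 135 and 180 child-months, so the first two could still influence conduct.
2. Reword the hospitalisation sentence to say that every hospitalisation, including for asthma, is recorded with its date on the case report form, whether or not it is classed as an SAE.
3. At each review, give the committee a cumulative listing of asthma hospitalisations, intensive-care admissions, emergency or urgent-care visits, oral steroid courses and terminations.
4. Reconcile the enrolment periods in Sections 5 and 8.

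**Cost.** Two or three short meetings of existing personnel, one dated field and one data listing. Treatment, study visits and the individual termination rule are unchanged.

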17. PAYMENT FOR PARTICIPATION: *

This compensation is for reimbursement of time for the parent/guardians and participants for time spent in visit and as an honorarium for their ongoing participation.

All compensation given to participants will be in the form of ClinCard. A ClinCard is a reloadable debit card. Incentives will be loaded onto the card after each visit according to the payment schedule. Participants will receive a handout to explain the use of the card. Participants will receive a graduated amount to facilitate retention.

Parent/guardians will receive \$20 for completing questionnaires at the baseline visit.

We will provide the participants with payment as they progress through the study visits.

Visits	Amount
V1	\$100
V2	\$20
V3	\$25
V4	\$30
V5	\$35
V6	\$40
V7	\$150

Self Management Only Visits	Amount
1 ½ month Visit	\$30
2 month Visit	\$30
2 ½ month Visit	\$30
3 month Visit	\$30
3 ½ month Visit	\$30

For the Study Visit 2-7: We will also provide the participant with a meal or snack valued at approximately \$10 from a local restaurant such as Subway, Chipotle or Chick-Fil-A. An additional \$10 or an item valued at approximately \$10 will be given if Propeller caps are returned each month to place on new inhalers.

For the Adherence Only visits: We will also provide the participant with a meal or snack valued at approximately \$10 from a local restaurant such as Subway, Chipotle or Chick-Fil-A.

For Study Visit 7: The participant will be given the cell phone used in the study to keep but the data plan will be stopped and reset to factory settings.

For Post-Visit Surveys:

All participants who complete their response to the Post-Visit Surveys (subject, parent, school nurses) will receive \$10 added to their ClinCard. Nurses may be approached and asked follow-up questions regarding their perceptions of the study (see appendix X).

Appendix A. Propeller Health System.

PROPELLER

Hello, Alex! [Sign Out](#)

Madison | Air Quality: **Good** | 71° | The Weather Channel

This Week at a Glance

Degree of Asthma Control: Good 😊	Atrovent Last sync: 10/25/2012	Rescue Events 2	You're doing well this week! Keep it up!
Flovent Last sync: 10/25/2012	Control Medication Adherence 75%	Your monthly adherence is lower than it should be.	Over Time ■ Atrovent ■ Flovent

Alerts

No Alerts

Dust Mites

Give all of your bedding a hot wash at least once a week, and dry it thoroughly. Use dust-proof covers for pillows and mattresses.

[Read More...](#)

My To-Dos

Here are some suggestions for you to follow to manage your asthma care.

30% of the way there!

- Regularly dust to remove allergens from your home.
- Don't forget to use your doctor-prescribed control inhaler.
[Set a reminder](#)
- Reduce tobacco use.

Events in the Last 30 Days

Community Trends

77% Users Having Events	Exercise Most Common Trigger	Difficulty Breathing Most Common Symptom
-----------------------------------	--	--

5. In the PAST 12 months, because of asthma, how many times has the patient:

	Number of Times
(1). Needed to stay in the hospital overnight	0
(2). Gone to the emergency room or urgent care center	0
(3). Had Oral Steroids (Prednisone or Prednisolone, methylprednisolone, any dose, for less than 10 days)	0
(4). Gone to the Intensive Care Unit	0

Save Done Local intranet | Protected Mode: Off 100%

Appendix C. Asthma Control Tests. (ACT will only be used for ages 12 and up)

Enter Name _____
Enter Address _____
Enter City/State/Zip _____

Today's Date: _____

Patient's Name: _____

FOR PATIENTS:

Take the Asthma Control Test™ (ACT) for people 12 yrs and older.

Know your score. Share your results with your doctor.

Step 1 Write the number of each answer in the score box provided.

Step 2 Add the score boxes for your total.

Step 3 Take the test to the doctor to talk about your score.

1. In the past 4 weeks, how much of the time did your asthma keep you from getting as much done at work, school or at home?						SCORE 
All of the time  1	Most of the time  2	Some of the time  3	A little of the time  4	None of the time  5		
2. During the past 4 weeks, how often have you had shortness of breath?						
More than once a day  1	Once a day  2	3 to 6 times a week  3	Once or twice a week  4	Not at all  5		
3. During the past 4 weeks, how often did your asthma symptoms (wheezing, coughing, shortness of breath, chest tightness or pain) wake you up at night or earlier than usual in the morning?						
4 or more nights a week  1	2 or 3 nights a week  2	Once a week  3	Once or twice  4	Not at all  5		
4. During the past 4 weeks, how often have you used your rescue inhaler or nebulizer medication (such as albuterol)?						
3 or more times per day  1	1 or 2 times per day  2	2 or 3 times per week  3	Once a week or less  4	Not at all  5		
5. How would you rate your asthma control during the past 4 weeks?						
Not controlled at all  1	Poorly controlled  2	Somewhat controlled  3	Well controlled  4	Completely controlled  5		
						TOTAL 

Copyright 2002, by QualityMetric Incorporated.
Asthma Control Test is a trademark of QualityMetric Incorporated.

**If your score is 19 or less, your asthma may not be controlled as well as it could be.
Talk to your doctor.**

FOR PHYSICIANS:

The ACT is:

- A simple, 5-question tool that is self-administered by the patient
- Recognized by the National Institutes of Health
- Clinically validated by specialist assessment and spirometry¹

Reference: 1. Nathan RA et al. J Allergy Clin Immunol. 2004;113:596S.
